Randomized trial of holding vs. continuing incretin-based therapies before upper endoscopy

Principal Investigator:

[name].

Email: [contact]

Address: [name]

Background:

Incretin-based therapies include GLP-1 receptor agonists (GLP-1RAs) and dual GLP1-RA and gastric inhibitory polypeptide (GIP) agonists. These drugs are commonly prescribed for diabetes and more recently, their use has risen exponentially as a primary therapy for weight loss. These medications can decelerate gastric emptying and diminish bowel motility by inhibiting peristalsis at the GLP-1 receptors situated in myenteric neurons. Therefore, there exists a theoretic potential for gastroparesis, retained gastric contents, perioperative regurgitation, and pulmonary aspiration syndrome, and this is a concern for anesthesiologists and patients taking these medications.

The American Society of Anesthesiologists recently released a consensus-based statement that recommends patients on daily dosing hold incretin-based therapy the day of the procedure, and those on weekly dosing hold the medication a week before the procedure. The evidence for these recommendations is based on retrospective studies and case reports, and therefore the conclusions may be overly prescriptive. Furthermore, holding incretin-based therapy poses a risk for worsening diabetes control and more importantly, could cause unnecessary delays in care if a patient's procedure is postponed because they failed to hold the medication based on the recent recommendations (1-3).

Study Objective:

To assess whether holding incretin-based therapy before endoscopy reduces the likelihood of clinically relevant Residual Gastric Volume (RGV).

Hypothesis:

Holding incretin-based therapy is non-inferior to continuing incretin-based therapy for reducing the risk of clinically relevant RGV.

Study design:

Randomized Non-Inferiority Controlled Trial.

Blinding:

Single-blind: endoscopist and anesthesia team will be blinded to study group assignment.

Primary Outcomes:

The primary outcome is clinically significant residual gastric volume defined as a composite of the following variables:

- Residual gastric volume that precludes adequate endoscopic examination
- Residual gastric volume that necessitates premature termination of the endoscopy procedure
- Need for endotracheal intubation due to stomach contents.

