 - For patients who are not scheduled via the above route, a letter of invitation will be sent to the patient from the physician completing the procedure through the US mail or MyChart.
- Patient consent
 - Interested patients in the clinic setting will be given the option to complete a research encounter during the same day, including in-person consent if interested, or complete the process remotely over the phone and through MyChart Electronic consent, or DocuSign.
 - Patients who are not identified in clinic but through chart review will receive a phone call and phone encounters will be completed with interested potential participants and will include an explanation of the study and the consent process (phone scripts attached). MyChart Electronic consent process or DocuSign will be used to send the study consent to the participants.
- After obtaining consent, the patient information will be entered into the REDCap which will give the patient a REDCap serial number.

- A randomization tool in the REDCap will determine the intervention (The randomization table of allocation will be completed by a statistician on REDCap to ensure concealed allocation).
- The patient will be informed about the intervention during the clinic visit by a study member (not the endoscopist) or over the phone.
- A few days before the intervention, the patient will receive a call as a reminder of the intervention and instruction from a study member (not the endoscopist).
- On the endoscopy day, the proceduralist and anesthesia team will be blinded to the patient's group assignment. To ensure that blinding is maintained, a sticker will be placed on the patient physical chart to remind the provider to avoid asking about the study intervention.
- A research coordinator/investigator will confirm intervention compliance and record the variables of interest for the study.
- Information will be directly entered into the Redcap data collection sheet or recorded on a physical paper-based collection sheet and transferred immediately to Redcap on the same day. The physical sheets will be shredded on the day of the procedure.
- A phone call to the patient within the first week after the procedure to follow up and exclude aspiration events. If patient cannot be contacted, then a member of the study team will review patient records to identify any emergency department visits or hospitalizations related to a post-procedure aspiration event.

Electronic Consent operation

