- An investigator or research coordinator will contact the invited candidates over the phone 2-4 weeks before the scheduled procedure. The study purpose, intervention, adverse events, and consenting process will be discussed over the phone. The encounter will be documented in the patient chart as a phone encounter.
- Subjects interested in the study will be provided with consent through MyChart Electronic consent or DocuSign with instructions to complete online consent signing.
- After all parties complete the consent, a randomization of the study intervention will be done through Redcap.
- A follow-up phone call will be made to communicate the instructions to the participants.

Rational for electronic consent (E-consent)

The study is not feasible with conventional consent, especially for open access procedures for the following reasons:

- The duration for participant involvement in the study is short, and the study intervention is only applied one week before the procedure, which would make it impractical to bring the patient for an extra encounter and would decrease the chance for enrollment.

- Many procedures are scheduled in an open-access fashion, which means that the patient is scheduled for the procedure by a provider other than the performing physician and/or from a different department.
- The intervention for the study must be completed one week before presenting to the procedure, which requires that the patient be enrolled before the procedure date.

Sample Size Determination:

- Previous retrospective studies indicate that 5-7% of GLP-1RA users have increased RGV compared to less than 0.5% in non-users.
- If there is a significant difference in favor of the experimental (“hold”) group of 7%, then 120 patients are needed (60 in each group) to be 80% certain that the upper limit of a one-sided 95% confidence interval (or equivalently a 90% two-sided confidence interval) will exclude a difference in favor of the standard group of more than 3% (the non-inferiority limit) using Farrington-Manning’s score test.
- Because estimates from previous retrospective studies are for the outcome of residual gastric volume, they may not accurately reflect our primary outcome, which is a more pragmatic and clinically useful outcome. Therefore, we plan to conduct an interim analysis at 20% recruitment and may adjust sample size if necessary, based on point estimates derived from the interim analysis.

Study Variables

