Date of birth, gender, race, body mass index (BMI), type of incretin-based therapy used, incretin therapy dose, pre-endoscopy clinical symptoms, presence of diabetes, last HbA1c if available, detailed endoscopic reports, gastric residual content on endoscopy, and RGC-related events as described above. Please refer to the data collection sheet for details of the variables above.

Study Statistics

The Statistics will be done with the help of a Cleveland Clinic statistician. Data will be extracted in deidentified form directly from Redcap for analysis.

Once data has been collected, we will use STATA version 14.1 (STATA Corp, College Station, TX, USA) for statistical analysis. We will use statistics of central tendency (mean, median, and mode) for most values. Data normality will be tested using Kolmogorov-Smirnov test. We will use Pearson’s chi-square tests for categorical variables and T-test for continuous variables. A P-value of < 0.05 will be considered significant for all statistical analyses. The primary outcome will be calculated using chi-square or Mann-Whitney test. For the primary outcome, an intention-to-treat analysis will be utilized.

Interim Analysis and Data Monitoring Committee (DMC)

The study DMC will include the following: The gastroenterology program director at Weston, a gastroenterologist, and a Cleveland Clinic statistician. Meetings will be held at 20%, 50, and 100% of recruitment to ensure data security compliance, appropriate rate of recruitment, and study adverse events monitoring. A report of each meeting will be sent to the IRB. The DMC will not be blinded for study groups. Interim analysis will be conducted after 20 and 50% of recruitment on the second DMC meeting, and the study will be stopped if inferiority is confirmed.

Data Security

Data, including patient information and consent, will be stored electronically in the Redcap system\DocuSign which is password-protected and on the secure Cleveland Clinic network. If physical paper sheets were used, the physical paper sheets' information would be transferred to Redcap and shredded on the day of data gathering.

Possible Harm to Subjects and Adverse Events

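### Intention-to-treat is the only analysis set named for the primary non-inferiority outcome, and the compliance that staff confirm enters no stated analysis; a supportive per-protocol analysis should be pre-specified (minor).

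*Combined protocol and SAP*

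**What the plan says.** The Hypothesis section frames the trial as non-inferiority: "Holding incretin-based therapy is non-inferior to continuing incretin-based therapy for reducing the risk of clinically relevant RGV". Sample Size Determination plans 60 patients per group for 80% assurance that the upper limit of a one-sided 95% interval, by the Farrington-Manning score test, "will exclude a difference in favor of the standard group of more than 3% (the non-inferiority limit").

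Study Statistics names one analysis set: "For the primary outcome, an intention-to-treat analysis will be utilized". The same section gives chi-square or Mann-Whitney as the test for the primary outcome. It names no per-protocol or as-treated set and does not define adherence.

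Compliance is nevertheless checked. Study Operation says: "A research coordinator/investigator will confirm intervention compliance and record the variables of interest for the study". The item follows the one about the endoscopy day, so the check appears to happen then. The list under Study Variables does not mention compliance, but it ends "Please refer to the data collection sheet for details of the variables above". That sheet is not among the documents, so a compliance field may already exist.

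**The concern.** Patients carry out the intervention at home, on an instruction given in clinic or by phone. Some in either arm may not follow it. Under intention-to-treat, each such patient moves the two arms' risks closer together.

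The effect depends on which regimen is better. The plan assumes that hold is better, and the section on possible harm places the study risk with continuing. In that direction crossover shrinks a real benefit and costs power. If hold were worse by as much as the 3-point limit, crossover would hide part of the harm and make a non-inferiority claim somewhat easier.

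Interpretation is what is at stake. If non-inferiority is not shown, the planned report will not help separate a true difference from non-adherence. If it is shown, the report will not say whether the result also holds among patients who followed their assignment. A complier set chosen after the results are known would carry little weight.

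**Working it through.** **Inputs.** From Sample Size Determination: 60 per arm, one-sided 5%, margin m = 0.03, and event rates "5-7% of GLP-1RA users have increased RGV compared to less than 0.5% in non-users". Assumed: crossover c of 10% or 20%, unrelated to a patient's own risk. The documents give no rate.

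**1. The plan's own sample size.** Take hold pH = 0.005 and continue pC = 0.07. The Farrington-Manning large-sample formula is

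n = [(1.645·s0 + 0.842·s1) / (m − (pH − pC))]²

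where s0 uses the rates constrained to differ by 0.03 (0.0658 and 0.0358), giving s0 = 0.310, and s1 = √(0.005·0.995 + 0.07·0.93) = 0.265. The denominator is 0.03 + 0.065 = 0.095, and n = 59.5, so 60 per arm. The planned figure reproduces, with power of 80%. (These rates differ by 6.5 points, not the stated 7. A 7-point difference gives 60 with a hold rate near 0.87%.)

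**2. Exact power without crossover.** I summed binomial probabilities over every outcome in which the Farrington-Manning test claims non-inferiority. The test claims it with at least 1, 3 or 5 continue events when hold has 0, 1 or 2. Exact power is 92.3%, above the large-sample 80% because events are few.

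**3. Dilution.** pH* = (1 − c)·pH + c·pC. If both arms cross over, also pC* = (1 − c)·pC + c·pH. For example, at c = 20%, pH* = 0.8·0.5% + 0.2·7% = 1.8% and pC* = 0.8·7% + 0.2·0.5% = 5.7%.

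| True rates, hold vs continue | No crossover | 10%, hold only / both arms | 20%, hold only / both arms |
|---|---|---|---|
| Power, 0.5% vs 7% | 92.3% | 82.5% / 79.1% | 72.0% / 63.0% |
| Power, 0.5% vs 5% | 84.2% | 74.4% / 71.0% | 65.1% / 57.4% |
| False claim, 10% vs 7% | 4.8% | 5.4% / 6.0% | 6.0% / 7.5% |
| False claim, 8% vs 5% | 5.0% | 5.7% / 6.4% | 6.5% / 8.1% |
| False claim, 5% vs 2% | 5.1% | 6.0% / 7.1% | 7.1% / 9.7% |
| False claim, 3.5% vs 0.5% | 3.2% | 3.8% / 5.8% | 4.5% / 9.2% |

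A false claim here concerns the regimens as taken. The last two rows put continue below the documents' rates for users. With no true difference, crossover changes nothing (14.9% at 7% vs 7% throughout).

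**4. What a per-protocol set can and cannot do.**
- Size: with 10% or 20% non-compliance in both arms, about 54 or 48 per arm remain. Power is 76% or 71% by the large-sample formula, and 86% or 79% exact.
- Requiring both sets to pass: with crossover in both arms, only 76% (10%) or 59% (20%) of 150,000 simulated trials succeed under the assumed benefit.
- Selection: suppose 20% of the hold arm do not hold and have twice the compliers' risk r. From 0.8r + 0.2·2r = 10%, r = 8.3%. A true 3-point excess over 7% then appears as 1.3 points, and false claims are 8.4% per-protocol against 7.1% for intention-to-treat.

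**The case against.** Intention-to-treat answers a sensible pragmatic question, namely the effect of telling patients to hold or continue, and its test level for that question is unaffected by crossover. Per-protocol can mislead more, as the selection example shows. The power lost to crossover is not recovered by adding a second table. At 10% crossover with 0.5% vs 7%, exact power is still 79-83%, about what was planned, and the reminder call may keep crossover low. With 5-7% of 60, only 3 to 4 continue-arm events are expected, so a difference between the two sets can turn on one event. Counts of non-compliance by arm would already answer much of the question.

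All of this stands. It limits the point to a supportive analysis and makes it minor, but does not remove it: counts alone do not show the estimate among compliers.

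Three stronger readings are tempting, and the documents do not support them.
- A reader might infer that intention-to-treat is the wrong primary set for non-inferiority, or seriously inflates error. In the plan's assumed direction the effect is lost power, and in the other direction the rise is modest.
- A reader might infer that nobody can be classified because hold is undefined. The Randomization section defines hold by the ASA guidance, which Background summarises as "patients on daily dosing hold incretin-based therapy the day of the procedure, and those on weekly dosing hold the medication a week before". The differing sentence, "The intervention for the study must be completed one week before presenting to the procedure", sits in the e-consent rationale. The wording needs reconciling, but it does not block classification.
- A reader might infer that compliance is not recorded. The missing data collection sheet leaves that open.

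**Conclusion.** The omission is real and minor. One analysis set is named, and confirmed compliance feeds no stated analysis. Under the plan's assumed benefit, 20% crossover would cost 20 points of exact power (92.3 − 72.0, hold arm only) to 29 points (92.3 − 63.0, both arms). If hold were worse by 3 points (10% vs 7%), the same crossover would add about 1 to 3 points to the false-claim rate.

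These sizes rest on assumed crossover rates, on non-compliance unrelated to risk, on the Farrington-Manning test rather than the test Study Statistics names, and on event rates that Sample Size Determination itself says may not reflect the primary outcome. Lower true rates could move the figures either way.

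The stated sample size is not in question here. The exclusion of patients who broke fasting instructions, which becomes known only after randomisation, affects who belongs in the intention-to-treat set. It is a separate issue and does not carry this point.

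**What to change.** Keep intention-to-treat as primary, and add to Study Statistics:

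1. The number and proportion non-compliant, by arm.
2. A supportive per-protocol analysis of patients whose confirmed compliance matches their assigned arm, classified without knowledge of outcome.
3. The risk difference and one-sided 95% Farrington-Manning upper limit against the 3% margin, shown for both sets side by side.
4. If the per-protocol limit does not exclude 3%, a statement that non-inferiority is not supported in compliers. This is not a second pass criterion.
5. An open statement that chi-square and Mann-Whitney do not test the 3% margin, and that the method in Sample Size Determination replaces them for the primary comparison in both sets.

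Also check that the data collection sheet holds a compliance field, reconcile the one-week wording in the e-consent rationale with the guidance-based hold in Background and Randomization, and say separately how fasting exclusions after randomisation are handled in the intention-to-treat set.

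The cost is SAP wording, one further analysis of information already gathered, and an explicit change to the named primary test. The downside is that the per-protocol set is smaller, rests on few events and is open to selection bias. It is supportive only and does not restore the power that crossover takes from intention-to-treat.

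### The only formal stopping rule does not say which arm must be inferior; as most naturally read it is practically inert against the harm the protocol names, and its timing contradicts the meeting schedule

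*Combined protocol and SAP*

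**What the plan says.** All references are to the combined protocol and SAP.

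- **Interim Analysis and Data Monitoring Committee (DMC).** The stopping rule is one clause: "the study will be stopped if inferiority is confirmed". It gives no arm, test or threshold. Meetings are set at 20%, 50% and 100% of recruitment, and the DMC is unblinded. The same section states: "Interim analysis will be conducted after 20 and 50% of recruitment on the second DMC meeting".
- **Hypothesis.** "Holding incretin-based therapy is non-inferior to continuing incretin-based therapy".
- **Sample Size Determination.** Hold is called the experimental group. The trial is sized so that a one-sided 95% limit from a Farrington-Manning score test "will exclude a difference in favor of the standard group of more than 3% (the non-inferiority limit"). The background rates are "5-7% of GLP-1RA users have increased RGV compared to less than 0.5% in non-users", with the caution that "they may not accurately reflect our primary outcome". A 20% look appears here too, for another purpose: "we plan to conduct an interim analysis at 20% recruitment and may adjust sample size if necessary".
- **Study Statistics.** The primary outcome is to be tested by chi-square or Mann-Whitney, and P<0.05 is the criterion for every analysis.
- **Possible Harm to Subjects and Adverse Events.** The study risk is attributed to continuing therapy around the procedure. It is described as theoretical and without strong supporting evidence. Serious unexpected events go to the IRB promptly, and study-outcome events go to the IRB after each DMC meeting.

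**The concern.** A stopping rule should tell the committee, before it sees data, which result ends the trial. This one leaves the direction to inference, and the inference runs against the protocol's own statement of risk. If hold is the arm tested for non-inferiority, inferiority means too many events on hold. The events that the protocol worries about (aborted procedures, urgent intubation, aspiration) are expected on continue. A committee facing an excess on continue could in good faith decide that the rule applies, or that it does not.

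The timing adds a second doubt. If both looks wait for the second meeting, the rule is first applied at 60 patients, and the 20% look comes too late to inform a sample-size decision at 20%. If the 20% look belongs to the first meeting, the sentence is wrong as written.

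**Working it through.** **1. Direction implied by the plan's own sample size.** Inputs from Sample Size Determination: margin 3 points, one-sided alpha 0.05, power 80%, rates 7% (continue) and 0.5% (hold). With hold as the experimental arm, the null is hold minus continue = +0.03. The restricted estimates under that null are 0.0658 (hold) and 0.0358 (continue).

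- V0 = 0.0658×0.9342 + 0.0358×0.9642 = 0.0960; square root 0.3098
- V1 = 0.07×0.93 + 0.005×0.995 = 0.0701; square root 0.2647
- n per arm = (1.645×0.3098 + 0.8416×0.2647)² / (0.065 + 0.03)² = 0.536 / 0.009025 ≈ 59.5, so 60 per arm and 120 in total

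The stated 120 is reproduced with hold as experimental. This supports reading inferiority as hold worse. (The plan speaks of a 7% difference; 7% against 0.5% is a 6.5-point gap.)

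**2. Timing.** 20% of 120 = 24 patients (first meeting); 50% = 60 (second meeting); 100% = 120 (third meeting). Only the 50% look fits the second meeting. The gap between the looks is 60 − 24 = 36 patients.

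**3. What the rule can do at the 50% look.** Assume equal arms of 30 and an uncorrected chi-square with critical value 3.84.

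- 3 events against 0: 60×(3×30)² / (30×30×3×57) = 3.16, no stop
- 4 events against 0: 60×(4×30)² / (30×30×4×56) = 4.29, stop
- 6 events against 1: 4.04, stop; 5 against 1: 2.96, no stop

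At 7% (continue) and 0.5% (hold):

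- *Continue worse.* P(4 or more on continue) = 0.1550 and P(0 on hold) = 0.995^30 = 0.8604; the product is 0.1333. Adding P(1 on hold) × P(6 or more on continue) = 0.1297×0.0162 = 0.0021 gives 0.135.
- *Hold worse.* P(4 or more on hold) = 1.54×10⁻⁵ and P(0 on continue) = 0.93^30 = 0.1134; the product is 1.8×10⁻⁶.

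Full enumeration:

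| Continue vs hold | Fires if aimed at continue | Fires if aimed at hold |
|---|---|---|
| 5% vs 0.5% | 5.3% | 3.3 per million |
| 7% vs 0.5% | 13.5% | 1.8 per million |

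**4. Whether the unspecified test matters.** At 12 per arm, 3 against 0 gives a chi-square of 24×(3×12)² / (12×12×3×21) = 3.43, and 4 against 0 gives 4.80, so chi-square needs 4. A Farrington-Manning test of an excess above 3 points at one-sided 0.05 needs only 3 against 0. At 30 per arm both need 4 against 0, so the choice changes the outcome at the 20% look but hardly at the 50% look.

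**5. Cost of aiming chi-square at continue, at both looks** (12 then 30 per arm, continue-worse direction only):

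| Situation | Probability of stopping |
|---|---|
| Equal rates, 3% to 20% | 0.5% to 3.8% |
| True 3-point excess on continue (3.5% vs 0.5% up to 23% vs 20%) | 1.7% to 6.9% |
| 5% vs 0.5% | 5.3% |
| 7% vs 0.5% | 13.6% |

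**The case against.** Several points on the other side stand.

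- **There is a default test.** A reader might infer that the plan offers no test or threshold at all. Study Statistics does give chi-square or Mann-Whitney at P<0.05 for all analyses, which can be read to include the interim. What remains is narrower: the default is not tied to the stopping rule, gives no direction, and differs from the one-sided score limit used for sizing.
- **Only the harm section truly conflicts with the inferred direction.** A reader might also cite the study objective and the assumed advantage of hold. Neither is a contradiction. A non-inferiority design may expect its experimental arm to do better, and the objective says nothing about stopping. The harm section itself calls the risk theoretical.
- **The 2-in-a-million figure is partly built in.** Any rule aimed at hold will almost never fire when hold is assumed far better. The figure shows that the rule is inert in the scenario the plan expects, and no more. Re-aiming it gains only 5.3% to 13.5% at the plan's rates.
- **The continue arm is not unmonitored.** That stronger reading is unsupported: an unblinded DMC reviews adverse events at every meeting, including the one at 24 patients, and the IRB receives reports.
- **The 36-patient delay is conditional.** It arises only if the formal rule is withheld at the 20% meeting and the sample size is not changed there. The text does not settle this.

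None of this supplies the missing arm or reconciles the second meeting with two looks.

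**Conclusion.** The point holds. The only formal stopping rule does not name its arm. On the reading best supported by the hypothesis and sample size, it has about 2 chances in a million of firing at the 50% look at 7% vs 0.5%, against 13.5% if aimed at continue (5.3% at 5% vs 0.5%). The placing of both looks on the second meeting is a contradiction on the face of the text.

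The size is limited. Even a well-aimed rule detects little at these rates, and discretionary DMC review and IRB reporting partly cover the gap. The plan should be corrected, but the documents do not support a claim that participants on continue are unprotected.

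The figures assume equal arms at each look (the plan uses simple randomization), primary-outcome rates equal to the retrospective residual-volume rates (which the plan doubts), and hold patients behaving like non-users. The missing arm and the timing conflict rest on the text alone.

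**What to change.** Reconcile the Hypothesis, Sample Size Determination, interim/DMC and harm sections so that the stopping rule:

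1. covers an excess of primary-outcome events in the continue arm, consistent with the harm section;
2. is tied to one stated test and threshold. The chi-square at P<0.05 already in Study Statistics, applied in the continue-worse direction, would suffice;
3. states whether it applies at the 20% meeting, the 50% meeting or both, and how the 20% look relates to the sample-size adjustment.

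A new score-test boundary is not needed. At 7% vs 0.5% over both looks, a score test against 3 points with a one-sided 95% limit detects 14.8%, against 13.6% for chi-square, but with more false stops (0.7% to 6.6% at equal rates of 3% to 20%). A 97.5% limit detects only 5.0%.

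The cost is protocol and DMC wording, plus the small false-stop probability tabulated above. The sponsor should accept that probability explicitly and recognize that detection at the plan's own rates stays modest (about 5% to 14%).
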